# Safety and Effectiveness of the Treatment of Wide Neck, Saccular Intracranial Aneurysms with the Neuroform Atlas™ Stent System

## Short Study Name: ATLAS

Reference	N	Neck <4mm	Neck ≥4mm	Dome-to-Neck Ratio	Ruptured	Location	Coiling BAC SAC	Anz Coiled (Anz at FUP)	Immediate Complete Occlusion ALL	Immediate Complete Occlusion WNA	Complete Occlusion at Follow-Up ALL	Complete Occlusion at Follow-Up WNA	Recanaliz n /Retreatment ALL	Recanaliz n /Retreatment WNA	Time to Follow-Up Angio Mean (Range)
2014 Hetts AJNR [26]	361 pts total; 224 pts coiled	73/224 (33%) were wide-neck anz			None	N/A	224/361 (62%) coiling	All = 224 anz; WNA = 73 anz (All = 180 anz; WNA = 59 anz)	76/224 (34%)	20/73 (27%)	80/180 (44%)	16/59 (27%)	19/224 (8%)	10/73 (14%)	Clinical = 1yr, 2yr Angio = 12 ± 3mo
2014 Hetts AJNR [26]	361 pts total; 137 pts SAC	85/137 (62%) were wide-neck anz			None	N/A	137/361 (38%) SAC	All = 137 anz SAC; WNA = 85 anz SAC (All = 114 anz; WNA = 70 anz)	29/137 (21%)	16/85 (19%)	59/114 (52%)	32/70 (46%)	12/137 (9%)	12/85 (14%)	Clinical = 1yr, 2yr Angio = 12 ± 3mo
2014 Liu J Clin Neurosci [69]	235 anz 235 pts with coiling (& 56 anz 56 pts SAC)	Mostly Wide-neck (Mean neck width for coiled anz = 4.08 ± 2.85mm)			165/235 (70%)	100% PComA	81% Coiling 19% SAC	235 anz (203 anz)	N/A	83/235 (35%)	N/A	103/203 (51%)	N/A	57/203 (28%)	13.2 ± 9.5 mo = mean angio FUP
2014 Peterson Neurosurg [42]	35 anz 35 pts with BAC; (& 71 anz 71 pts with SAC)	100% Wide-neck			None	89% Ant 11% Post	35/106 (33%) = BAC; 71/106 (67%) = SAC	35 anz (35 anz)	N/A	18/35 (51%)	N/A	19/35 (54%)	N/A	2/35 (6%)	Angio FUP at 6mo and 12 mo
2015 Song J Korean Neurosurg Soc [70]	53 anz 53 pts	100% Wide-neck			28/53 (53%)	17% AComA 9% MCA Bifurc n 8% Cavernous 26% Paracclinoid 19% PComA 8% Basilar Tip 13% Unk	85% Coiling 15% SAC	45 anz coiling alone; 8 anz SAC (45 anz coiling alone; 8 anz SAC)	N/A	25/45 (56%)	N/A	20/45 (44%)	N/A	15/45 (42%) = major recurrence; 7/45 (16%) = minor recurrence; 8/53 (15%) = retreatment	Angio FUP 37.9 mo (12 - 120 mo)
2011 Modi Interv Neuroradiol [40]	11 anz 11 pts	100% Wide-neck			6/11 (55%)	64% Ant 36% Post	100% BAC	11 anz (11 anz)	N/A	8/11 (73%)	N/A	8/11 (73%)	N/A	1/11 (9%)	11 mo (6-20 mo)

N = sample size; BAC = balloon-assisted coiling; SAC = stent assisted coiling; Anz= aneurysm; FUP = follow-up; ALL = all aneurysms studied; WNA = wide neck aneurysm; Angio = angiography/angiogram; pts = patients; ant = anterior circulation; post = posterior circulation; N/A = not available; mo = months; yr = years; PComA = posterior communicating artery; AComA = anterior communicating artery; MCA = middle cerebral artery; Bifurcn = bifurcation; Unk = unknown

[figure not shown]
# Safety and Effectiveness of the Treatment of Wide Neck, Saccular Intracranial Aneurysms with the Neuroform Atlas™ Stent System

## Short Study Name: ATLAS

### Random Effect Model Meta-Analyses

Two random effect model meta-analyses were performed in order to determine overall complete occlusion rates of treated aneurysms at final follow-up. One meta-analysis was performed using complete occlusion data from published literature only, with data from the article by Hetts et al being used as data from the MAPS study. This meta-analysis included data for coiling alone, balloon-assisted coiling, and stent assisted coiling, with the latter coming from articles by Hetts et al and Chalouhi et al. For this meta-analysis, data specific to wide neck aneurysms yielded an average weighted complete occlusion rate of 49% (Figure 3). The second meta-analysis was performed using complete occlusion data from published literature for coiling and balloon assisted coiling in combination with complete occlusion data for coiling only subjects from the previously described MAPS wide neck aneurysm patient cohort (N = 247). For this meta-analysis, data specific to wide neck aneurysms yielded an average weighted complete occlusion rate of 47% (Figure 4). Given the findings of these two meta-analyses, a historical control rate of 50% for complete occlusion is conservative and is justified.

### Complete Occlusion Rate

[figure not shown]
### Meta Analysis (Random effect)

**Figure 3 - Complete Occlusion Rates, Wide Neck Intracranial Aneurysms Only, MAPS Data from Hetts et al., Includes Stent Assisted Coiling Data from Hetts et al. and Chalouhi et al.**

# **Safety and Effectiveness of the Treatment of Wide Neck, Saccular Intracranial Aneurysms with the Neuroform Atlas™ Stent System**

## **Short Study Name: ATLAS**

### **Complete Occlusion Rate**

#### **Meta Analysis (Random effect)**

**Figure 4 - Complete Occlusion Rates, Wide Neck Intracranial Aneurysms Only, MAPS Data from MAPS Dataset, Includes Coiling or Balloon Assisted Coiling Data Only**

### **4.5.2 Justification of Safety Criteria**

#### Data from the MAPS Trial

As presented in **Table 5**, analysis of the 12-month ( $\pm 3$  months) safety data from the previously described MAPS wide-neck aneurysm patient cohort ( $N = 247$ ) showed that the overall stroke rate was 6.9% (17/247), and in the anterior and posterior subgroups, the stroke rates were 5.9% (12/205) and 11.9% (5/42), respectively ( $P = 0.18$ ). There was one neurological death, which occurred in the anterior circulation subgroup (0.5%). When stroke and neurological death rates were combined, the overall incidence rate was 7.3% (18/247).

# **Safety and Effectiveness of the Treatment of Wide Neck, Saccular Intracranial Aneurysms with the Neuroform Atlas™ Stent System**

## **Short Study Name: ATLAS**

**Table 5 - MAPS Cohort - Primary Safety Outcomes**

Primary Safety Outcomes	Wide Neck Aneurysms [1,2] (N =247)		P-value
	Anterior Non-petrous (n =205)	Posterior (n =42)	
Stroke [3]	5.85% (12/205)	11.90% (5/42)	0.1787
Neurological Death	0.49% (1/205)	0.00% (0/42)	1.0000
Composite of Stroke and Neurological Death	5.85% (12/205)	11.90% (5/42)	0.1787

[1] Neck width  $\geq$  4mm or dome-to-neck ratio  $< 2$

[2] Excludes subjects with a pre-procedure Hunt and Hess score  $\geq 3$ ; excludes subjects with a pre-procedure mRS score  $\geq 4$

[3] Includes strokes of any type or severity

Safety data from the MAPS wide neck aneurysm patient cohort are consistent with the primary safety endpoints that have been chosen for each cohort in this study. Assuming a primary safety endpoint of 8% in the anterior circulation cohort and 12% in the posterior circulation cohort, the upper limit of the 95% confidence interval of the proportion of subjects who achieve the primary safety endpoint is  $<20.0\%$  and  $<25.0\%$  in each cohort, respectively.

### Data from the Scientific Literature

The 11 articles located via the comprehensive literature search that was performed to locate relevant historical effectiveness data were likewise used to develop objective performance benchmarks against which the safety results of this study could be measured. A summary of safety data derived from these articles is presented in **Table 6**.

A review of these articles yielded ranges for procedural complication rates (1% - 36%), procedural morbidity (mRS  $\geq 3$ ) rates (0% - 17%), procedural neurologic mortality rates (0% - 9%), stroke rates through follow-up (0% - 12%), long-term morbidity (mRS  $\geq 3$ ) rates (2% - 13%), and long-term neurologic mortality rates (2% - 10%) for all aneurysms that were treated using embolic coiling, balloon-assisted embolic coiling, or stent assisted coiling. For the sub-set of wide neck aneurysms that were treated using embolic coiling, balloon-assisted embolic coiling, or stent assisted coiling, long-term morbidity and mortality rates ranged from 0% - 25%.

Again, given these findings, the success criteria for safety that have been chosen for this study (i.e., upper limit of the 95% confidence interval of the proportion of subjects with anterior or posterior circulation aneurysms who achieve the primary safety endpoint is  $< 20\%$  and  $< 25\%$ , respectively) are within range and appropriate.

# Safety and Effectiveness of the Treatment of Wide Neck, Saccular Intracranial Aneurysms with the Neuroform Atlas™ Stent System

## Short Study Name: ATLAS

**Table 6 - Summary of Safety Data Derived from Literature Search**

Reference	N	Neck <4mm	Neck ≥4mm	Dome-to-Neck Ratio	Ruptured	Location	Coiling BAC SAC	Procedural Complications	Procedural Morbidity (mRS ≥3)	Procedural Neurologic Mortality	Stroke (Procedure Thru Follow-up)	Long-Term Morbidity (mRS ≥3)	Long-Term Neurologic Mortality	Long-Term Morbidity & Mortality for WNA Subset	Follow-Up Period Mean (Range)		
2000 Aletich JNS [37]	75 anz 72 pts	52/75 (69%)	23/75 (31%)	53/75 (71%) = <2 22/75 (29%) = ≥2	20/75 (27%)	75% Ant 25% Post	100% BAC	7/72 (10%); 2 = anz rupture 1 = TE stroke	4/72 (6%)	3/72 (4%)	2/72 (3%)	N/A	N/A	7/72 (10%)	11.2 mo (6-29 mo)		
2001 Cottier AJNR [39]	45 anz 44 pts	100% Wide-neck anz			27/44 (61%)	95% Ant 5% Post	100% BAC	2/44 (5%); 2 = TE	0/44 (0%)	0/44 (0%)	0/44 (0%)	N/A	N/A	N/A	16 mo (3 mo - 5 yr)		
2001 Nelson AJNR [41]	22 anz 22 pts	100% Wide-neck anz			9/22 (41%)	100% Ant	100% BAC	7/22 (3.2%); 1 = minor stroke 2 = groin hematomas 1 = groin pseudoaneurysm 1 = TE 2 = TIA (1 in pt who also had a groin hematoma)	1/22 (5%)	2/22 (9%)	1/22 (5%)	N/A	N/A	2/22 (5%)	angio 19 mo clinical 29 mo		
2002 Lozier Stroke [30]	495 anz 489 pts (meta-analysis of 12 studies)	40%	60% Wide-neck anz		19%	100% Post	100% Coiling	62/489 (13%); 13 = rupture 14 = coil protrusion 27 = thrombosis 5 = embolism 3 = dissection	25/489 (5%)	7/489 (1% procedural); 33/489 (7% at 30 days)	N/A	24/450 (5%)	44/450 (10%)	N/A	16.8 mo (mean for 6/12 studies) and 26.1 mo (mean for 6/12 studies)		
2006 Niimi Stroke [31]	74 anz 70 pts	43/74 58%	10/74 (14%) = Small wide-neck 20/74 (27%) = Large (assumed to be wide-neck) 1/74 (1%) = Giant (assumed to be wide-neck)		31/74 (42%)	80% Ant 20% Post	79% Coiling 16% BAC 5% SAC	12/70 (17%); 4 = TE events 4 = coil protrusion 1 = thrombus, extravasation (death) 3 = asymptomatic	1/70 (1%)	1/70 (1%)	2/70 (3%); 1 = TE 1 = delayed rupture	8/62 (13%)	3/62 (5%)	N/A	15 mo (1-37 mo)		
2013 Chalouhi AJNR [38]	101 pts total; 32 BAC	100% Wide-neck			21/32 (66%)	81% Ant 19% Post	32/101 (32%) BAC	3/32 (9%); 1 = rupture 1 = thrombus 1 = infarct	1/32 (3%)	N/A	1/32 (3%)	N/A	N/A	1/32 (3%); permanent morbidity	Angio FUP 6.5 mo (3 - 36 mo)		
2013 Chalouhi AJNR [38]	101 pts total; 69 SAC	100% Wide-neck			8/69 (12%)	84% Ant 16% Post	69/101 (68%) SAC	4/69 (6%); 1 = rupture 2 = clinical infarct 1 = silent infarct	2/69 (3%)	N/A	3/69 (4%)	N/A	N/A	2/69 (3%); permanent morbidity	Angio FUP 8.0 mo (5 - 48 mo)		

# Safety and Effectiveness of the Treatment of Wide Neck, Saccular Intracranial Aneurysms with the Neuroform Atlas™ Stent System

## Short Study Name: ATLAS

Reference	N	Neck <4mm	Neck ≥4mm	Dome-to-Neck Ratio	Ruptured	Location	Coiling BAC SAC	Procedural Complications	Procedural Morbidity (mRS ≥3)	Procedural Neurologic Mortality	Stroke (Procedure Thru Follow-up)	Long-Term Morbidity (mRS ≥3)	Long-Term Neurologic Mortality	Long-Term Morbidity & Mortality for WNA Subset	Follow-Up Period Mean (Range)
2014 Hetts AJNR [26]	361 pts total; 224 pts coiled	73/224 (33%) were wide-neck anz		None	N/A	224/361 (62%) coiling	All coiled anz 10/224 (5%) Coiled WNA 1/73 (1%)	N/A	N/A	All coiled anz 5/224 (2%) = ischemic stroke; 1/224 (<1%) = delayed rupture Coiled WNA 3/73 (4%) = ischemic stroke; 0/73 (0%) = delayed rupture	5/202 (3%)	4/202 (2%)	1/66 (2%) morbidity; 0/66 (0%) mortality	Clinical = 1yr, 2yr Angio = 12 ± 3mo	
2014 Hetts AJNR [26]	361 pts total; 137 pts SAC	85/137 (62%) were wide-neck anz		None	N/A	137/361 (38%) SAC	All SAC anz 9/137 (7%) SAC WNA 3/85 (4%)	N/A	N/A	All SAC anz 12/137 (9%) = ischemic stroke; 4/137 (3%) = delayed rupture SAC WNA 10/85 (12%) = ischemic stroke; 2/85 (2%) = delayed rupture	2/128 (2%)	3/128 (2%)	0/73 (0%) morbidity; 0/73 (0%) mortality	Clinical = 1yr, 2yr Angio = 12 ± 3mo	
2014 Liu J Clin Neurosci [69]	235 anz 235 pts with coiling (& 56 anz 56 pts SAC)	Mostly Wide-neck (Mean neck width for coiled anz = 4.08 ± 2.85mm)		165/235 (70%)	100% PComA	81% Coiling 19% SAC	27/235 (11%); 9 = TE 5 = rupture 13 = coil protrusion	39/235 (17%); oculomotor nerve paresis	N/A	N/A	N/A	N/A	53/211 (25%)	13.3 ± 9.3 mo for 211/235	
2014 Peterson Neurosurg [42]	35 anz 35 pts with BAC; (& 71 anz 71 pts with SAC)	100% Wide-neck		None	89% Ant 11% Post	35/106 (33%) = BAC; 71/106 (67%) = SAC	3/35 (9%) = minor complications (groin complications, asymptomatic vessel dissection)	0/35 (0%)	0/35 (0%)	0/35 (0%)	N/A	N/A	0/35 (0%)	Mean 24.5 mo; 6 and 12 mo angios	
2015 Song J Korean Neurosurg Soc [70]	53 anz 53 pts	100% Wide-neck		28/53 (53%)	17% AComA 9% MCA Bifurc n 8% Cavernous 26% Paraclinoid 19% PComA 8% Basilar Tip 13% Unk	85% Coiling 15% SAC	6/53 (11%); 2 = TE (1 resolved, 1 infarction) 2 = aneurysm rupture 1 = occluded ophthalmic (flow restored at FU) 1 = coil migration	1/53 (2%)	0/53 (0%)	1/53 (2%); cerebral infarction	N/A	N/A	0/53 (0%)	Angio 37.9 mo (12 - 120 mo)	
2011 Modi Interv Neuroradiol [40]	11 anz 11 pts	100% Wide-neck		6/11 (55%)	64% Ant 36% Post	100% BAC	4/11 (36%); 3 = local thrombus 1 = dissection 1 = groin hematoma	0/11 (0%)	0/11 (0%)	0/11 (0%)	N/A	N/A	0/11 (0%)	11 mo (6-20 mo)	

N = sample size; BAC = balloon-assisted coiling; SAC = stent-assisted coiling; WNA = wide neck aneurysms; anz = aneurysms; pts = patients; Ant = anterior circulation; Post = posterior circulation; TE = thromboembolic; N/A = not available; mo = months; yr = years; TIA = transient ischemic attack; Angio = angiography/angiogram; FUP = follow-up; mm = millimeters; PComA = posterior communicating artery; AcomA = anterior communicating artery; MCA = middle cerebral artery; Bifurcn = bifurcation; Unk = unknown; FU = follow-up

## **Safety and Effectiveness of the Treatment of Wide Neck, Saccular Intracranial Aneurysms with the Neuroform Atlas™ Stent System**

### **Short Study Name: ATLAS**

#### **4.6 Statistical Analysis**

All analyses will be performed using SAS, version 9.4 or higher. Some interim analyses and figures may require the use of R 3.2.3 or above.

Primary analysis will initially be carried out when data from 153 evaluable subjects from the mITT group of anterior circulation subjects are available.

Due to the substantially lower incidence of aneurysms in the posterior circulation (approximately 15-20% of diagnosed cases), the subject enrollment period for the posterior circulation cohort will be much longer in duration versus that of the anterior circulation cohort. As a result, analysis of data from the posterior circulation cohort will be completed after results for the anterior circulation subjects have already been submitted for review by the FDA, and data from that analysis will be used to support an expanded indication for use of the Neuroform Atlas™ Stent System, i.e. an indication for use in the posterior circulation. For the posterior circulation cohort, a Bayesian adaptive study design (“Goldilocks” approach) providing for interim analyses of accumulated data will be used to select the final sample-size. The first interim data analysis will occur once 100 posterior circulation subjects have been enrolled. Based on enrollment rates and the frequency of disease in the posterior circulation, at the time this interim analysis is performed it is estimated that primary endpoint data will be available for approximately 39 – 63 posterior circulation subjects. If, at an interim analysis, there is at least a 95% predictive probability of observing a true rate of complete occlusion that is higher than 50%, enrollment in the posterior circulation cohort will be stopped early for success. The maximum sample-size for the posterior circulation cohort will be no more than 180 subjects.

Analyses for both cohorts will be performed by constructing two-sided 95% confidence intervals about the estimates of the percentage of subjects with complete aneurysm occlusion and the percentage of subjects experiencing a major ipsilateral stroke or neurological death using the exact binomial (Clopper-Pearson) method. For the effectiveness endpoint of total occlusion, the lower bound of this confidence interval will be compared to 50% for both the anterior and posterior circulation cohorts. For the safety endpoint of major ipsilateral stroke and neurological death, the upper bound of the confidence interval will be compared to 20% for the anterior circulation cohort, and 25% for the posterior circulation cohort.

Success requires safety and effectiveness endpoints to be met in each cohort separately. Success in the anterior cohort occurs when the lower bound of the effectiveness endpoint is above 50% and the upper bound of the safety endpoint is below 20%. Success in the posterior cohort occurs when the lower bound of the effectiveness endpoint is above 50% and the upper bound of the safety endpoint is below 25%.

The analysis of long-term safety and effectiveness data will be descriptive only, as no formal hypotheses will be tested based on data collected during this phase of the study. Survival analysis will be used to estimate the incidence of specified safety endpoint events, as well as retreatment of the target aneurysm. Details regarding the survival analyses are summarized in **Table 7**.

**Safety and Effectiveness of the Treatment of Wide Neck, Saccular Intracranial Aneurysms with the Neuroform Atlas™ Stent System**

**Short Study Name: ATLAS**

**Table 7 – Endpoint Measure Definitions in the Post-approval Study**

	Survival Analysis		Incidence Rate		% Subjects who Experienced the Outcome [2]			
	Competing Risk [1]	Event	Numerator	Denominator	Numerator	Denominator		
Primary Safety Outcome	Non-neurologic death	Death	Number of events (N1)	Person-time based on follow-up date (D1)	Number of subjects who experienced new outcome in the interval (N2)	Number of subjects present for one or more visits during or after the interval or experienced outcomes during the interval (D2)		
Neurological death								
New or worsening major ipsilateral stroke								
Any ischemic or hemorrhagic AE(s)								
Hemorrhagic Stroke								
Ischemic Stroke								
SAH								
Aneurysm Rupture								
TIA								
Device-related SAE(s)								
Grade 1 Raymond class in the absence of retreatment, or parent artery stenosis (>50%) at the target location	N/A	N/A	N/A	N/A	Number of subjects who are not retreated and whose current DSA met the outcome definition	Number of subjects with valid DSA or underwent retreatment		
Retreatment	Death	The first event	N1	D1	N2	D2		
Raymond Class	N/A	N/A	N/A	N/A	Number of subjects whose current DSA met the outcome definition	Number of subjects with valid DSA		
Parent Artery Stenosis > 50%	N/A	N/A	N/A	N/A				
Recanalization	Death	The first event	N1	Person-time based on DSA date				
Stent Migration								
Progressive Occlusion of the Target Aneurysm	N/A	N/A	N/A	N/A				

[1] Subjects are censored on the date of the event; other censoring events include lost-to-follow-up, consent withdrawal, and study early discontinuations due to other reasons.

[2] Repeated for each visit interval, i.e. 2-year, 3-year, post-3-year intervals.

[3] The observational period for the survival analysis and incidence rate starts on the day after a subject's 12-month follow-up visit.

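### Table 7 names death as a competing risk but censors at it; if the survival columns are reported as one minus Kaplan-Meier, they would slightly overstate cumulative incidence

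*Combined protocol and SAP*

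**What the plan says.** Section 4.6 sets the aim of the long-term analysis: "Survival analysis will be used to estimate the incidence of specified safety endpoint events, as well as retreatment of the target aneurysm". It sends the reader to Table 7 for the details, and section 4.8 repeats the aim. Neither section names Kaplan-Meier, a cumulative incidence function or any other estimator.

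Under its survival-analysis heading, Table 7 has a column for competing risks. The entry for the primary safety outcome is "Non-neurologic death". The retreatment row reads, cell by cell, "Retreatment Death The first event", and recanalization has the same two entries. Note [1], attached to the heading of that column, gives the handling: "Subjects are censored on the date of the event; other censoring events include lost-to-follow-up". The note's list goes on to withdrawal of consent and other early discontinuation.

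Table 7 also defines two measures outside the survival columns: an incidence rate (events over person-time) and the percentage of subjects with the outcome in each visit interval. Its note [3] sets the time origin: "The observational period for the survival analysis and incidence rate starts on the day after a subject's 12-month follow-up visit". Sections 4.6 and 4.8 both state that the long-term analysis is descriptive and tests no hypothesis.

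**The concern.** A subject lost to follow-up can still be retreated or have a stroke, unobserved. A subject who has died cannot. Note [1] puts the two on the same footing: by speaking of other censoring events, it makes the competing death one more of them. The table therefore recognises the competing risk by name and then gives a rule that ignores it.

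One minus Kaplan-Meier with deaths censored estimates the risk in a setting where the competing death cannot occur. It is never below the cumulative incidence, and it is above it once competing deaths have removed subjects who could still have had the event. The stated target is incidence, so a reader of the post-approval report would take the figure as the share of treated patients who had the event by a given time. At stake is a modest upward distortion of safety, retreatment and recanalization figures intended for post-approval reporting to the FDA.

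**Working it through.** The plan states no long-term event rate, mortality or precision target, so it has no figure of its own to reproduce. The size has to be worked out under assumptions.

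**Inputs from the documents**
- Time origin: the day after the 12-month visit (Table 7, note [3]).
- Horizon: 3 years ± 6 months (section 2.1), hence 36 − 12 = 24 months or 42 − 12 = 30 months of observation (2 or 2.5 years). Table 2 adds a visit at 43-60 months for some subjects, hence up to 60 − 12 = 48 months (4 years).
- Maximum size: 360 subjects (section 2.2.2).

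**Assumed inputs, not in the documents**
- Constant event rate λ of 1-5% a year.
- Constant competing death rate μ of 0.5-5% a year.

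**Formulas**, with T years of observation:
- One minus Kaplan-Meier, censoring at the competing death: 1 − exp(−λT).
- Cumulative incidence: λ/(λ+μ) × [1 − exp(−(λ+μ)T)].

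Worked example with λ = 0.03, μ = 0.02, T = 2: one minus Kaplan-Meier is 1 − exp(−0.06) = 5.82%. Cumulative incidence is 0.6 × [1 − exp(−0.10)] = 5.71%. The excess is 0.11 points.

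| T (years) | λ, μ per year | 1 − KM | Cumulative incidence | Excess (points) |
|---|---|---|---|---|
| 2 | 1%, 0.5% (smallest) | 1.980% | 1.970% | 0.01 |
| 2 | 5%, 5% (largest) | 9.516% | 9.063% | 0.45 |
| 2.5 | 1%, 0.5% | 2.469% | 2.454% | 0.015 |
| 2.5 | 5%, 5% | 11.750% | 11.060% | 0.69 |
| 4 | 1%, 0.5% | 3.921% | 3.882% | 0.04 |
| 4 | 5%, 5% | 18.127% | 16.484% | 1.64 |

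A second set of assumptions, given as 2-year risks, agrees. Competing death of 2%, 6% and 10% paired with a Kaplan-Meier event risk of 5%, 10% and 14% gives cumulative incidences of 4.95%, 9.7% and 13.3%, so the excess is 0.05, 0.3 and 0.7 points.

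**Person-time rate.** Expected events per subject are λ/(λ+μ) × [1 − exp(−(λ+μ)T)]. Expected person-time, stopped at event, death or T, is [1 − exp(−(λ+μ)T)]/(λ+μ). The ratio is λ exactly, so stopping the clock at death does not inflate the rate. A simulation of 2,000,000 subjects with λ = 0.03 and μ = 0.02 gave 0.0302.

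**Scale against sampling error.** If all 360 subjects contributed, a simple binomial 95% half-width would be 1.96 × √(0.05 × 0.95/360) = 2.3 points at a 5% risk and 1.96 × √(0.14 × 0.86/360) = 3.6 points at 14%. The matching 2-year excesses are 0.05/2.3 = 2% and 0.7/3.6 = 19% of those half-widths. At the 4-year extreme the half-width is 1.96 × √(0.181 × 0.819/360) = 4.0 points, and 1.64/4.0 = 41%. With fewer subjects, or either cohort alone, these shares would be smaller.

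**The case against.** The strongest reply is that no estimator is named. Censoring at a competing event is the correct step for a cause-specific hazard, and the bias appears only when that hazard is turned into one minus Kaplan-Meier and read as a probability. This stands, and it is why the point is conditional. A reader might infer that the plan commits to a biased estimate; the documents do not go that far. They do give incidence as the target, censoring as the only handling, and a separate column for person-time rates, so one minus Kaplan-Meier is the natural way to fill the survival columns.

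A reader might also infer that all long-term results are affected. They are not. The person-time rate is unbiased by this rule. The percent-of-subjects measure does not use note [1]. The survival columns are marked N/A for the composite effectiveness measure, Raymond class, parent artery stenosis and progressive occlusion. The 12-month primary endpoints use exact binomial intervals.

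Three further replies have weight. No success criterion depends on these figures. For safety events, retreatment and recanalization, an overstatement would count against the device. Section 4.9 recognises informative censoring and plans sensitivity analyses on loss to follow-up, although it does not say how competing deaths are to be handled.

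Finally, merged cells in Table 7 did not survive text extraction. Which competing risk applies to each lower safety row cannot be read, and the death entry under the Event heading should not be called an error.

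**Conclusion.** The point holds in a limited form. Table 7 names death as a competing risk, note [1] censors at it, and section 4.6 promises incidence without naming an estimator. If the survival columns are reported as one minus Kaplan-Meier, they exceed cumulative incidence for the safety outcome, retreatment and recanalization. Under the assumed constant rates, the excess is about 0.01-0.7 points at 2 to 2.5 years and up to about 1.6 points at 4 years, a horizon only some subjects reach. The direction follows from the method; the size rests wholly on the assumed rates. This is a minor correction to a descriptive analysis. It does not show that the long-term results as a whole are biased, and it has no bearing on trial success.

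**What to change.** Amend Table 7, note [1], to say that the survival-analysis columns use the Aalen-Johansen cumulative incidence function, with the death listed for that row as a competing event. Keep censoring only for loss to follow-up, withdrawal of consent, early discontinuation and study end. Name the same estimator in sections 4.6 and 4.8, and leave the person-time incidence rate as it is. If the sponsor in fact means a cause-specific quantity, the table should say so and should not present it as incidence.

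The cost is one line of text plus the cross-references. No new data are needed, and the method is standard in SAS 9.4 and R, both already named in section 4.6.
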